1. GLOSSARY OF TERMS AND ABBREVIATIONS

AE	Adverse Event
CI	Chief Investigator
CRF	Case Report Form
CPAP	Continuous Positive Airway Pressure
DMC	Data Monitoring Committee
EQ5D	EQ5D is a standardised questionnaire for measuring quality of life and a trademark of the Euro-Qol group
ICF	Informed Consent Form
ICU	Intensive Care Unit
JRMO	Joint Research Management Office
NHS REC	National Health Service Research Ethics Committee
NHS R&D	National Health Service Research & Development
Participant	An individual who takes part in a clinical trial
PI	Principal Investigator
PIS	Participant Information Sheet
QA	Quality Assurance
QC	Quality Control
RCT	Randomised Controlled Trial
REC	Research Ethics Committee
SAE	Serious Adverse Event
SDV	Source Document Verification
SOP	Standard Operating Procedure
SSA	Site Specific Assessment
TMG	Trial Management Group
TSC	Trial Steering Committee

3. SUMMARY

Short title	PRISM trial
Methodology	International, multi-centre randomised controlled trial with open study group allocation.
Research sites	Hospitals undertaking elective intra-peritoneal surgery in participating countries.
Objectives	To determine whether early postoperative continuous positive airway pressure (CPAP) reduces the incidence of subsequent respiratory complications and improves one-year survival following major intra-peritoneal surgery.
Number of patients	4800 patients
Inclusion criteria	Patients aged 50 years and over undergoing major elective intra-peritoneal surgery.
Statistical analysis	The primary outcome measure is a composite of pneumonia, re-intubation, or death within 30 days of randomisation. The analysis will be conducted according to intention-to-treat principles; all participants with a recorded outcome will be analysed according to the treatment group to which they were randomised. The primary outcome will be analysed using a mixed-effects logistic regression model, which includes centre as a random-intercept, and will be adjusted for the minimisation factors and other pre-specified baseline covariates.
Proposed start date	October 2015
Proposed end date	October 2019
Trial duration	48 months

4. INTRODUCTION

Approximately 310 million surgical procedures are carried out worldwide each year.¹ After surgery more than seven million patients develop complications with one million deaths.² Estimates of postoperative mortality range from 1 to 4% depending on the population sampled and the type of surgical procedure.³ However, it is clear that mortality and morbidity following surgery is greater in high-risk cohorts, where patients have pre-existing medical conditions, are elderly or undergoing a major abdominal procedure, for example surgery to the gastrointestinal tract.⁴ The lasting impact of postoperative morbidity should not be underestimated, since complications following surgery are associated with reduced long-term survival.^{5, 6} Some of the most common postoperative complications affect the respiratory tract.⁷ The published incidence of postoperative pulmonary complications ranges from 9 to 40%, depending on the definition used.^{8, 9}

Major abdominal surgery is associated with adverse changes in respiratory function. Anaesthesia can cause reduced vital capacity, hypoxaemia and impaired central respiratory drive, while surgical manipulation can restrict ventilation, damage the respiratory muscles and cause atelectasis.¹⁰ These factors interact with pre-existing respiratory disease and postoperative pain to create a significant risk of pneumonia and respiratory failure, which may result in death. Evidence from one study suggests that the risk of mortality within 30 days of surgery is increased from 1% to 27% in patients with respiratory failure.⁸ Usual treatments including supplemental oxygen or respiratory physiotherapy may not always prevent deterioration in respiratory function. Subsequent respiratory failure can lead to endotracheal intubation and mechanical ventilation, which is in turn associated with a range of serious morbidities.

Continuous positive airway pressure (CPAP) is a non-invasive method of supporting respiratory function. The patient breathes through a pressurized circuit against a threshold resistor that maintains a pre-set positive airway pressure during both inspiration and expiration.⁹ It is delivered via a facemask, helmet or nasal device by experienced nurses with minimal physician supervision.¹¹ CPAP is often provided in specialist areas of a hospital such as the critical care unit due to the benefit of increased staff numbers. However, this intervention could also be provided on a surgical ward, provided suitably trained nursing staff are available.⁹ The findings of several trials have demonstrated the efficacy of CPAP as a preventative treatment for

high-risk patients following abdominal surgery by reducing the incidence postoperative pulmonary complications. This is supported by evidence from systematic reviews, which call for further research in this area (figure 1).^{9, 12, 13} However, the current evidence base for postoperative CPAP has a number of limitations. Firstly, all of the previous randomised trials have been relatively small ($n < 250$) and therefore lacking in statistical power for patient centered outcomes. Whilst the results of these trials suggest that postoperative CPAP is efficacious, there has yet to be a large multi-centre trial to evaluate the clinical effectiveness of this treatment. Secondly, whilst the several trials of CPAP in the abdominal surgery population have shown encouraging results, there has been limited translation to clinical practice.¹¹ A robust evidence base is needed to justify the changes needed in the perioperative care pathway, and as a result the preventive use of CPAP after major abdominal surgery has not been introduced into routine practice in most healthcare systems. There is a clear need for a major randomised trial to provide definitive evidence to address this uncertainty.

[figure not shown]

Figure 1. Efficacy of CPAP on a composite endpoint of postoperative pulmonary complications compared to standard treatment.¹²

Current evidence suggests that the routine use of postoperative CPAP is an efficacious preventative treatment that can reduce postoperative respiratory complications. However, evidence of clinical effectiveness is lacking. In particular postoperative CPAP needs to be studied in the context of routine clinical care with reference to patient-centred outcomes. We propose a large, pragmatic, international multi-centre trial to confirm the clinical effectiveness of CPAP administered as routine for four hours immediately following major abdominal surgery, compared to usual clinical care.

5. TRIAL OBJECTIVES

5.1 Primary objective

To determine whether postoperative continuous positive airway pressure (CPAP) reduces the incidence of pneumonia, re-intubation or death following major elective intra-peritoneal surgery compared to usual care in patients aged 50 years and over.

5.2 Primary outcome measure

Composite endpoint of pneumonia, endotracheal re-intubation or death within 30 days of randomisation (Appendix).

5.3 Secondary objectives

To determine whether routine postoperative CPAP reduces other forms of postoperative morbidity, mortality, or improves quality of life.

5.4 Secondary outcome measures

- Pneumonia within 30 days of randomisation
- Endotracheal re-intubation within 30 days of randomisation
- Death within 30 days of randomisation
- Postoperative infection within 30 days of randomisation
- Mechanical ventilation (invasive or non-invasive) within 30 days of randomisation
- All-cause mortality at one year after randomisation
- Quality adjusted life years (QALY) at one year after randomisation

In addition, we will use the following process measures (i.e. non-patient centred outcome measures), to facilitate comparison with other research:

- 30-day re-admission
- Days in critical care
- Duration of hospital stay

5.5 Safety objectives

To determine the safety and tolerability of routine postoperative CPAP.

5.6 Safety outcome measures

Safety outcomes will quantify harm associated with CPAP (appendix). The following pre-defined adverse events will be measured within 24 hours of the end of surgery in patients in the intervention group only:

- Interface intolerance due to excessive air leaks
- Pain
- Cutaneous pressure sore or pressure area
- Claustrophobia
- Oro-nasal dryness
- Hypercapnia
- Haemodynamic instability
- Vomiting
- Aspiration of gastric contents
- Other harm assessed as probably or definitely related to CPAP

A full list of definitions is available in the appendix.

6. METHODOLOGY

6.1 Study design

International, multi-centre randomised controlled trial with open study group allocation.

6.2 Inclusion criteria

[figure not shown]
Patients aged 50 years or over undergoing elective major intra-peritoneal surgery using an open surgical technique.

6.3 Exclusion criteria

- Inability or refusal to provide informed consent
- Anticipated requirement for invasive or non-invasive mechanical ventilation for at least four hours after surgery as part of routine care
- Pregnancy or obstetric surgery
- Previous enrollment in PRISM trial
- Current participation in a clinical trial of a treatment with a similar biological mechanism or related primary outcome measure

- Clinician refusal
- Contraindication to continuous positive airway pressure (CPAP)

6.4 Study flow diagram

7. TRIAL PROCEDURES

7.1 Recruitment and screening

This is an international randomised controlled trial. Potential participants will be screened by research staff at the site having been identified from pre-admission clinic lists, operating theatre lists and by communication with the relevant nursing and medical staff. Before surgery, potential participants will be identified and approached by a member of the research team, who are considered part of the direct care team. Wherever possible, the patient will be approached at least 24 hours prior to surgery to allow time for any questions. However, by the nature of the inclusion criteria for this trial, many patients will arrive in hospital on the morning of surgery. Provided that all reasonable efforts have been made to identify a potential participant 24 hours in advance of surgery, they will still be eligible for recruitment within a shorter time frame if this has not proved possible. Written informed consent must be obtained before surgery.

7.2 Informed consent

It is the responsibility of the Principal Investigator (PI) at each site, or persons delegated by the PI to obtain written informed consent from each subject prior to participation in this trial. This process will include provision of a patient information sheet accompanied by the relevant consent form, and an explanation of the aims, methods, anticipated benefits and potential hazards of the trial. The PI or designee will explain to all potential participants that they are free to refuse to enter the trial or to withdraw at any time during the trial, for any reason. If new safety information results in significant changes in the risk/benefit assessment, the patient information sheet and consent form will be reviewed and updated if necessary. However, given the short duration of the intervention period, it is most unlikely that new safety information would come to light during the intervention period of an individual patient. Patients who lack capacity to give or withhold informed consent will not be recruited. Patients who are not entered into this trial should be recorded (including reason not entered) on the patient-screening log in the PRISM Investigator Site File.

7.3 Randomisation

Patients will not be randomised before giving written informed consent. Randomisation will be performed immediately after surgery (up to four hours after the

end of the surgical procedure). Participants will be centrally allocated to treatment groups (1:1) by a computer generated dynamic procedure (minimisation) with a random component. Minimisation variables will be country, surgical procedure category and planned use of epidural anaesthesia. The surgical procedure categories are: resection of colon, rectum or small bowel; resection of liver, pancreas or gall bladder; resection of stomach (non-obesity surgery); obesity surgery; vascular procedure; or other intra-peritoneal procedure. Each participant will be allocated with 80% probability to the group that minimises between group differences in these factors among all participants recruited to the trial to date, and to the alternative group with 20% probability. To enter a patient into the PRISM trial, research staff at the site will log on to a secure web-based randomisation and data entry platform and complete the patient's details to obtain a unique patient identification number and allocation to a treatment group. Investigators will declare the intended postoperative care destination before randomisation. This will measure changes in postoperative care that could be attributed to the delivery of the intervention.

7.4 Trial intervention

The trial intervention period will ideally commence immediately after surgery. This will allow widespread implementation of the treatment in post-anaesthetic recovery units, without the need for critical care admission, or other major changes in the perioperative care pathway. After four hours, CPAP will be continued or discontinued at the clinician's discretion.

Intervention group

The trial intervention is defined as CPAP for at least four hours, with minimal interruption, ideally started within four hours after the end of surgery. Where the start of CPAP has been delayed by exceptional circumstances (e.g. equipment failure, critical care admission, etc.), the intervention may be commenced up to twelve hours after the end of surgery. Administration of CPAP will only take place under the direct supervision of appropriately trained staff in an adequately equipped clinical area. Delivery of the trial intervention and monitoring of patients receiving CPAP will be in accordance with local hospital policy or guidelines. Alterations to the administered dose will be recorded along with the reason for this change. Investigators may only use CPAP equipment approved for routine use in their hospital to deliver the

intervention. The starting airway pressure should be 5 cmH₂O and the maximal permissible airway pressure is 10 cmH₂O. The airway pressure may be adjusted within this range at the discretion of the responsible physician. For example, it may be deemed beneficial to increase the airway pressure above 5 cmH₂O for patients with obesity or low chest wall compliance. Since this is a pragmatic clinical effectiveness trial additional training or standardisation of the intervention will not be provided.

[figure not shown]
Nasal high flow oxygen is not considered CPAP. It is foreseeable that some patients in the intervention group will not receive CPAP or fail to complete the minimum four hours of CPAP, e.g. due to unplanned invasive or non-invasive ventilation after surgery or because the patient is unable to tolerate the CPAP mask. These situations will be managed as protocol deviations and follow-up data will still be collected. Please see section 7.8 for further details.

Usual care group

Patients in the usual care group will be managed by clinical staff according to local policy and guidelines. The trial findings will therefore reflect the fact that usual care may differ between participating centres, and indeed this is one of the purposes of large clinical effectiveness trials. It is considered good practice for postoperative patients to receive oxygen via a facemask or nasal cannulae. However, this may vary according to local policy. The use of mechanical ventilation, recruitment manoeuvres or high flow nasal oxygen during the intervention period will be recorded on the case report form. It is foreseeable that some patients in the usual care group could receive CPAP as part of usual care. This will be managed as a protocol deviation and follow-up data will still be collected. Please see section 7.8 for further details.

7.5 Intervention algorithm

This algorithm illustrates the steps for delivering postoperative CPAP to patients in the intervention group. Patients in the usual care group will receive postoperative care according to local guidelines. Further details are listed in the CPAP SOP.

7.6 Procedures to minimise bias

It is not possible to conceal treatment allocation from all staff in trials of this type. However, procedures will be put in place to minimise the possibility of bias arising because research staff become aware of trial group allocation. Patients will be followed up for complications by a member of research staff who is unaware of trial group allocation. Complications will then be verified by the local PI or designee who will also be unaware of trial group allocation. The local principal investigator may nominate a senior clinician to assist with this task if he/she becomes aware of the trial group allocation of any individual patient. During the course of follow-up it is possible that a member of the research team may become aware of the treatment group allocation. To quantify the degree of blinding, research staff will make a self-assessment of blinding when collecting follow-up data. The decision to admit a trial participant to a critical care unit will be made by clinical staff and this decision must not be affected by trial group allocation.

7.7 Data collection

The following data will be collected from all sites before and after the trial intervention. Component data will be collected to calculate the ARISCAT score.¹⁴

Randomisation data

- Checklist to ensure the patient meets the eligibility criteria
- Surgical procedure category
- Centre ID
- Planned use of epidural anaesthesia

Baseline data

- Full name
- Gender
- Age/DOB
- ASA grade
- Planned surgical procedure
- Diagnosis of chronic lung disease (COPD, Asthma, Interstitial lung disease, bronchiectasis)

- Respiratory infection within the previous month (including tuberculosis)
- Diagnosis of ischaemic heart disease
- Diagnosis of diabetes
- Diagnosis of stroke
- Diagnosis of heart failure
- Diagnosis of cirrhosis
- Diagnosis of active cancer
- Diagnosis of Human Immunodeficiency Virus (HIV) infection
- Preoperative haemoglobin
- Preoperative creatinine
- Quality of life according to EQ-5D
- Height
- Weight
- NHS number or corresponding patient identifier for database follow-up
- Residential postcode or corresponding patient identifier for database follow-up

Intraoperative period

- Surgical procedure category
- Open technique used
- Anaesthetic technique (general, spinal, regional)
- Mechanical ventilation (Y/N)
 - Duration
 - Maximum PEEP
 - Maximum Vt
 - Maximum FiO₂ (excluding pre-oxygenation during induction of anaesthesia)
 - Total IV fluid input (sum of crystalloid and colloid)
 - Total blood product input (sum of all blood products)
- Extubated at the end of surgery (Y/N)
- Intraoperative recruitment manoeuvre (Y/N)

24 hours postoperative

- Patient received CPAP within twelve hours after the end of surgery? (Y/N)
 - Total duration of CPAP within 12 hours of surgery

- Delivery method (mask, nasal, helmet)
- Maximum airway pressure
- Additional research staff present to help deliver CPAP (Y/N)
- Were tools used to monitor CPAP and inspiratory oxygen fraction? (Y/N)
- Did the patient have a nasogastric tube *in situ* during CPAP? (Y/N)
- Did the patient receive high flow nasal oxygen? (Y/N)
- Adverse events during CPAP (tertiary outcomes)
 - Interface intolerance due to excessive air leaks (Y/N)
 - Pain (Y/N)
 - Cutaneous pressure sore or pressure area (Y/N)
 - Claustrophobia (Y/N)
 - Oro-nasal dryness (Y/N)
 - Hypercapnia (Y/N and peak PaCO₂)
 - Haemodynamic instability (Y/N)
 - Vomiting (Y/N)
 - Aspiration of gastric contents (Y/N)

Clinical outcomes within 30 days of randomisation

- Pneumonia (Y/N)
- Re-intubation (Y/N)
- Death (date)
- Mechanical ventilation (Y/N)
- Quality of life according to EQ5D

Health economic outcomes

- Duration of primary hospital stay
- Days in critical care during the first 30 days after index surgical procedure

Clinical outcomes within one year of randomisation

- Death (date)
- Quality of life according to EQ5D

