7.8 Predefined protocol deviations

- Failure to administer CPAP to patients in the intervention group. This includes patients that unexpectedly remain intubated after surgery, or where CPAP is started more than twelve hours after the end of surgery
- Starting CPAP at a dose other than 5 cmH₂O.
- Administration of CPAP to a patient in usual care group. If this occurs within 12 hours of the end of surgery, investigators should consider this a protocol deviation.
- Administration of CPAP for less than 4 hours duration for a patient in the intervention group.
- Administration of CPAP with significant interruption for a patient in the intervention group. Brief interruptions to CPAP to adjust mask, for oral care or routine nursing care are considered part of the intervention. However, if the interruption is prolonged this should be considered a protocol deviation. Investigators will make a judgement about whether the interruption is prolonged and encouraged to record the duration of any interruption on a protocol deviation form. As a guide, a continuous interruption of more than 15 minutes would usually be considered relevant.

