8.2 Statistical analysis

All analyses will be conducted according to intention-to-treat principles, meaning that all patients with a recorded outcome will be included in the analysis, and will be analysed according to the treatment group to which they were randomised. Baseline patient characteristics will be presented, stratified according to treatment allocation. The primary outcome (pneumonia, endotracheal re-intubation, or death within 30 days of randomisation) will be analysed using a mixed-effect logistic regression model. Centre will be included as a random-intercept, and the model will be adjusted for the minimisation variables (country, planned use of epidural anaesthesia and planned surgical procedure category (resection of colon, rectum or small bowel; resection of liver, pancreas or gall bladder; resection of stomach (non-obesity surgery); obesity surgery; vascular procedure; or other intra-peritoneal procedure) and planned use of epidural anaesthesia), as well as the following pre-specified baseline covariates: age, gender, co-morbid disease (chronic respiratory disease, ischaemic heart disease, diabetes mellitus, heart failure, liver cirrhosis, active cancer, and previous stroke or transient ischaemic attack), smoking status and ASA score. The significance level will be set at 0.05. A full statistical analysis plan will be

developed prior to analysis. Clinical outcomes are defined in appendix.

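### The CPAP duration item closes at 12 hours, the same point as the latest accepted start, so a full four-hour course begun after hour 8 is recorded as shorter than four hours

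*Protocol*

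**What the plan says.** Section 7.4 defines the intervention as "CPAP for at least four hours, with minimal interruption, ideally started within four hours after the end of surgery". It adds that, where exceptional circumstances cause delay, "the intervention may be commenced up to twelve hours after the end of surgery".

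Section 7.8 is consistent with this. A late start becomes a deviation only "where CPAP is started more than twelve hours after the end of surgery". A separate deviation is "Administration of CPAP for less than 4 hours duration for a patient in the intervention group", and no 12-hour limit is attached to that duration.

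Section 7.7, in the list for the 24-hour postoperative form, asks "Patient received CPAP within twelve hours after the end of surgery? (Y/N") and beneath it "Total duration of CPAP within 12 hours of surgery". This is the only duration item. The other CPAP entries cover the delivery method, maximum pressure, staffing, monitoring, nasogastric tube and adverse events. The list has no CPAP start time and no stop time.

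**The concern.** The window in which CPAP time is counted closes at the moment the window for starting CPAP closes. A patient can therefore start within the accepted period, complete the minimum course, and still have less than four hours in the database.

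Section 7.4 itself foresees patients who never receive CPAP or who stop before four hours. The delivered duration will therefore be needed to interpret the result, above all a null one: did the treatment not work, or was it not given? The affected patients are not a random subset either. Section 7.4 names equipment failure and critical care admission as reasons for delay, and the second of these is related to how ill the patient is. If the four-hour criterion were computed from this field, a compliant late course could not be told apart from one that was cut short.

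**Working it through.** The protocol gives no figure to reproduce here; the check is on time windows.

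**Inputs**
- Minimum course: 4 h (section 7.4).
- Latest accepted start: 12 h after the end of surgery (sections 7.4 and 7.8).
- Counting window of the duration item: 0 to 12 h after surgery (section 7.7).
- Period covered by the form: 24 h after surgery (section 7.7).
- CPAP group size: 2400 (section 8.1).

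**Most that the item can hold.** For an uninterrupted 4 h course started t hours after surgery:

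recorded hours = min(4, 12 − t)

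| Start t (h) | Hours given | Most that can be recorded | Shows 4 h? |
|---|---|---|---|
| 0 to 8 | 4 | 4 | yes |
| 9 | 4 | 3 | no |
| 10 | 4 | 2 | no |
| 11 | 4 | 1 | no |
| 12 | 4 | 0 | no |

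The shortfall begins where 12 − t < 4, that is, t > 8. Starts between 4 and 8 hours are later than the ideal in section 7.4 but are recorded in full. Short pauses that stretch the course over more than four hours of clock time would bring the threshold slightly earlier; they are ignored here.

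**Can the true duration be recovered?** Not from the listed items. The deviation form does not help: section 7.8 mentions it for recording interruptions, and a late starter who completes the course has no deviation to report.

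**How many patients?** The protocol does not say how many start after hour 8. With an assumed share q of the CPAP group who start then and complete four hours, the number under-recorded is q × 2400:
- q = 0.5%: 0.005 × 2400 = 12
- q = 1%: 0.01 × 2400 = 24
- q = 5%: 0.05 × 2400 = 120

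**Would a repaired item fit the form?** The latest accepted start plus the minimum course ends at 12 + 4 = 16 h, which is inside the 24-hour period.

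**The case against.** A reader might infer that these patients are logged as non-adherent, or that they meet the section 7.8 deviation automatically. The protocol does not support this. Section 7.8 concerns CPAP administered, sets no 12-hour limit on the four hours, and is not tied to the item in section 7.7. A patient who starts at hour 9 and completes four hours does not meet the deviation as written. Misclassification follows only if adherence is later derived from the section 7.7 field, and the protocol nowhere says that it will be.

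Four further objections deserve weight.

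- **Few patients.** Randomisation takes place within four hours of surgery, CPAP should ideally start at once, and longer delay is reserved for exceptional circumstances. The number is therefore probably small and may be close to zero. This stands, and it limits the importance of the point.
- **No stated analysis is harmed.** Under section 8.2, patients "will be analysed according to the treatment group to which they were randomised", and the protocol specifies no adherence-based analysis. This also stands.
- **Section 7.7 may not be the whole case report form.** Some data that the protocol says are collected, such as the intended care destination (7.3) and changes of dose (7.4), are not in its list. Sites must also know the start time in order to apply the 12-hour deviation. Start times may therefore exist in site records or on the form itself, which is not shown. That is possible, but the protocol does not require them as data.
- **The item may be shorthand.** It sits under the question on receipt of CPAP within 12 hours and could mean the length of the course begun in that window. If some sites read it so and others literally, the field would mean different things at different sites. That is a reason to clarify the wording, not to leave it.

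**Conclusion.** The point holds as a data item that is wrong as written, with limited reach. Taken literally, it cannot show four hours for an uninterrupted four-hour course begun more than 8 and up to 12 hours after surgery, although sections 7.4 and 7.8 accept such a course. The shortfall for a minimum course runs from just above 0 hours for a start just after hour 8 to the full 4 hours for a start at hour 12.

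The consequence is confined to the description of delivered duration, and to any adherence summary or adherence-based analysis that uses this field, for those patients only. The assumed range of 0.5% to 5% of the CPAP group, 12 to 120 patients, has no basis in the protocol beyond the fact that such starts are meant to be exceptional; the lower end is the more plausible. The mismatch between the windows does not depend on that share. The conclusion rests on a literal reading of the item and on section 7.7 listing all the CPAP timing data required.

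**What to change.** On the existing 24-hour form, replace the duration item with the start and stop date and time of the CPAP course begun within 12 hours of surgery. A single field would also do: the total duration of that course, counted to its end even where it runs past hour 12. Derive the four-hour criterion from this. Keep the yes/no item on receipt within 12 hours for both groups, because section 7.8 uses the same window for CPAP given in the usual care group. Tying the count to the course begun in the window is safer than counting all CPAP over 24 hours, which could add CPAP given later for other reasons.

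Sections 7.4, 7.7 and 7.8 should then be reconciled on this data item. No change to the permitted start time is implied.

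The cost is one field reworded or split and a line of guidance to sites. The sample size and the primary analysis are unchanged.
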